Noninfectious inflammatory myelopathies were previously often categorized as idiopathic transverse myelitis, but advances in neuroimaging and neuroimmunology have allowed more specific diagnoses, such as multiple sclerosis (MS) and neuromyelitis optica (NMO). With the exception of relapsing remitting multiple sclerosis (RRMS) there are no existing therapies that alter the course of these diseases. People with these disorders inexorably accumulate disability. In virtually every person with secondary progressive MS (SPMS) ambulation will be significantly affected leading to use of canes, walkers, and then wheelchairs. Functional electrical stimulation (FES) cycling is a method of applying low level electrical currents to the leg and buttock muscles to cause the weakened or paralyzed muscles to contract and produce a cycling motion of the legs. It has been used most in rehabilitation of patients with traumatic spinal cord injuries (SCI). Over the recent years FES cycling has become an increasingly important modality in rehabilitation of patients with paralysis. It has been shown to have multiple primary medical benefits including: increased muscle mass^{1,2}, improvements in bone density³, enhanced cardiovascular function⁴, improved bowel function⁵, decreased spasticity⁶ and reductions in bladder infection rate⁷. More importantly it has been shown to improve recovery from SCI. In a recent pilot trial [IRB protocol NA_00015238] with MS patients at our center we showed improvements on a broad array of functional and neurologic outcome measures including gait, upper extremity dexterity, and quality of life. Further, analysis of cerebrospinal fluid before FES and 3 months after initiating FES cycling revealed an enhanced neural repair program and a reduced inflammatory environment within the CNS. **One of the most important questions unanswered in regards to this technology is: How much FES is required to result in the most optimal recovery?** We currently use an experience based approach (3 to 5 FES cycling sessions per week, 1 hour each). From extensive clinical experience in our center, we suspect that the more FES is applied the better recovery is. In order to find the optimal dose of FES we identified a biomarker that can be measured in the spinal fluid of individuals receiving FES. **Brain derived neurotrophic factor (BDNF) levels correlate closely with functional recovery^{8,9}.** Voluntary exercise induces a BDNF-mediated mechanism and promotes neural plasticity in the CNS. **Currently, there are no controlled clinical trial data available on the effect of FES ergometry on neurotrophin release and functional recovery following neurological injury.** Our center specializes in chronic rehabilitation of patients with paralysis. In our clinical experience electrical stimulation leads to accelerated recovery of neurological function compared to traditional rehabilitation¹⁰. We speculate that this is in part due to local neurotrophin release resulting in neuroprotection and repair. It is unclear what the optimal "dose" of FES is, i.e., what dose is required for maximal recovery of function. **Here we propose to measure CSF BDNF concentrations in response to FES ergometry in patients with inflammatory myelopathies. In addition we will measure markers of inflammation in response to FES.** These data will be crucial for the design of a phase 3 clinical trial evaluating the efficacy of FES in patients with inflammatory myelopathies.

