Transverse myelitis (TM): TM is a focal inflammatory disorder of the spinal cord, resulting in motor, sensory, and autonomic dysfunction. It has an incidence of 1-4 new cases per million people per year, affecting individuals of all ages with bimodal peaks between the ages of 10 and 19 years and 30 and 39 years. There is no sex or familial predisposition to TM. It is characterized clinically by acutely or subacutely developing symptoms and signs of neurologic dysfunction in motor, sensory, and autonomic nerves and nerve tracts of the spinal cord. There is often a clearly defined rostral border of sensory dysfunction, and spinal MRI and lumbar puncture often show evidence of acute inflammation. When the maximal level of deficit is reached, approximately 50% of patients have lost all movements of their legs, virtually all patients have bladder dysfunction, and 80 to 94% of patients have numbness, paresthesias, or band-like dysesthesias. Autonomic symptoms consist variably of increased urinary urgency, bowel or bladder incontinence, difficulty or inability to void, incomplete evacuation, or bowel constipation. Longitudinal case series of TM reveal that approximately one third of patients recover with little to no sequelae, one third are left with moderate degree of permanent disability, and one third have severe disabilities¹³.

Neuromyelitis optica (NMO): NMO is a distinct inflammatory demyelinating disease consisting of optic neuritis in combination with a longitudinally extensive TM in which the spinal cord lesion extends over three or more vertebral segments, but usually without significant brain involvement. It is characterized by the NMO-IgG autoantibody marker, which targets the water channel aquaporin-4. NMO-related myelitis attacks differ from the partial myelitis of MS in that they are longitudinally extensive, centrally based within the cord, and usually causes more severe bilateral impairment. CSF inflammation during active NMO relapses can be dramatic, revealing marked pleocytosis and high protein. Neurological recovery from NMO myelitis is very limited as compared to MS.

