The discrepancies of the different BDNF levels might be explained by the difference of assays used. BDNF assays are now commercially available (RayBiotech, Norcross GA, USA). With this assay the minimum detectable dose of BDNF is typically less than 0.3 ng/ml without cross reactivity to other cytokines (Reproducibility - Intra-Assay: CV<10%, Inter-Assay: CV<12%).

4. Study Procedures

Study Design:

Phase 2 trial.

This selection study will be performed as a randomized, parallel Group Trial to determine the amount of FES ergometry required to achieve maximal CSF BDNF levels in individuals with inflammatory myelopathy.

Subjects will be randomized into 4 groups (FES1: 1 session of FES ergometry per week, FES3:3 sessions of FES ergometry per week, FES5: 5 sessions of FES ergometry per week, and Passive: 3 sessions of passive cycling per week). Session duration is 60 minutes. After obtaining a detailed physical and spasticity testing, baseline serum and CSF BDNF levels will be measured. The subjects will then receive

FES ergometry or passive cycling according to their group assignment for 3 weeks. At that time the subjects will return for a physical exam, spasticity testing, and repeat serum and CSF BDNF level testing. The primary investigator will be blinded to the results. The Study Time Line is found in Figure 1.

[figure not shown]

Figure 1: Study Time Line

Study Treatments

All activities will be conducted at INI and are supervised by a licensed physical therapist. This includes all cycling activities; all study procedures, the screening and final visits. Urine (for rapid urine pregnancy testing) will be sent to the Johns Hopkins Medicine (JHM) Pathology lab.

Functional Electrical Stimulation Ergometry

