Upon completion of the study, participants will be referred back to their treating SCI specialist who will be made aware of the treatment and follow-up. The same protocol will be followed for patients who terminate the study early. In the event of discontinuation due to adverse event, participants will be followed by the PI until resolution or stabilization of their adverse condition and then referred back to their treating SCI specialist.

5. Inclusion/Exclusion Criteria

Inclusion criteria

1. History of inflammatory myelopathy with onset at least 3 months prior.
2. Males and females between the ages of 18 and 65 years inclusive.
3. No FES ergometer (i.e. RT300 or equivalent) use within 4 weeks.
4. Ability to comply with procedures and follow-up.
5. Participants must be medically stable with no recent (1 month or less) inpatient admission for acute medical or surgical issues.
6. Access to a telephone with texting capabilities (SMS).
7. English language proficiency.

Exclusion criteria

1. Cardiovascular disease as defined by previous myocardial infarction, unstable angina, requirement for anti platelet agents, congestive heart failure, or stroke NYHA Class III or IV, history of arrhythmia with hemodynamic instability.
2. Uncontrolled hypertension (resting systolic BP>160mmHg or diastolic BP >100mmHg consistently).
3. History of epileptic seizures.

Date: May 10, 2016

Principal Investigator: [name].

Application Number: NA_00041441

4. Subjects who have a pacemaker, an implanted defibrillator or certain other implanted electronic or metallic devices other than baclofen pumps.
5. Subjects who are unwilling to agree to two CSF examinations (lumbar punctures).
6. Unstable long bone fractures of the lower extremities.
7. Pregnancy.
8. Subjects having Stage 2 or greater sacral decubitus ulcer.
9. Subjects with history of inability to tolerate electrical stimulation.
10. Malignancy.
11. Active drug or alcohol use or dependence that, in the opinion of the site investigator, would interfere with adherence to study requirements.

6. Drugs/ Substances/ Devices

- a. The rationale for choosing the drug and dose or for choosing the device to be used.
- b. Justification and safety information if FDA approved drugs will be administered for non-FDA approved indications or if doses or routes of administration or participant populations are changed.
- c. Justification and safety information if non-FDA approved drugs without an IND will be administered.

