After enrolling 48 subjects (12 per group) we will estimate 2 quantities: the mean BDNF CSF level per group and the within group standard deviation of BDNF levels (averaged across the 4 groups). The sample size may then be adjusted based on the estimated effect size (estimated mean per treatment group - 80% of that estimated mean) and the estimated standard deviation. If the recalculated total sample size is equal or less than 100 then the study will proceed. Otherwise the study will be terminated at that point.

The required sample size will be computed such that it provides 80% probability of correctly selecting the amount of FES that yields the highest mean BDNF given a true 20% mean difference between the highest mean and the next highest mean.

Analysis plan:

Dependent Variables: CSF BDNF concentration, Serum BDNF concentration, CSF GDNF concentration, CSF NT-3 concentration, CSF NT-4 concentration, CSF CNTF concentration, CSF NGF concentration, CSF IL-6 concentration, CSF IL17 concentration, CSF TNF α concentration, CSF IL-1 β concentration, CSF IL-23 concentration, CSF IL-12 concentration, modified Ashworth score, mood.

Independent Variables: Intervention (FES ergometry); Timing

Approach: The distributions of all outcome variables (CSF BDNF concentration, Serum BDNF concentration, CSF GDNF concentration, CSF NT-3 concentration, CSF NT-4 concentration, CSF CNTF concentration, CSF NGF concentration, CSF IL-6 concentration, CSF IL17 concentration, CSF TNF α concentration, CSF IL-1 β concentration, CSF IL-23 concentration, CSF IL-12 concentration, modified Ashworth score, mood) will be described by treatment group (mean, median, standard deviation). The group that has the highest mean change in BDNF concentration will be used for further studies (future Phase 3 clinical trial).

Exploratory analysis will be performed to compare mean values of GDNF, NT-3, NT-4, CNTF, NGF, IL-6, IL17, TNF α , IL-1 β , IL-23, IL-12 concentration among the 4 groups using analysis of variance or suitable non-parametric methods (Kruskal-Wallis Test) if the outcome appears to be non-normally distributed.

- d. Early stopping rules.

The principal investigator may discontinue the study if the interim statistical analysis as described above indicates that the number of subjects required for this trial exceeds #80.

Patients may withdraw from the study at any time for any reason. Any investigator may discontinue a patient for any of the following reasons:

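### Diagnosis (MS, TM, NMO, other) enters neither the stated randomisation nor the arm ranking; if it affects change in CSF BDNF, the plan loses precision, mainly as extra subjects or termination at the cap

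*Combined protocol and SAP*

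**What the plan says.** The first inclusion criterion (section 5) is "History of inflammatory myelopathy with onset at least 3 months prior". It sets no diagnostic category, quota or cap. Section 3 describes MS, transverse myelitis and NMO as separate diseases and notes, for example, that "Neurological recovery from NMO myelitis is very limited as compared to MS".

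Section 4, Study Design, states that "Subjects will be randomized into 4 groups". The documents describe no randomisation method, blocking or stratification factor.

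Section 7.c lists intervention and timing as the only independent variables and describes every outcome by treatment group. The decision rule is "The group that has the highest mean change in BDNF concentration will be used for further studies". No covariate enters it.

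The sample size is re-estimated once: "After enrolling 48 subjects (12 per group) we will estimate 2 quantities". These are the group mean of CSF BDNF and the within-group SD, averaged over the four arms. The target is an 80% probability of selecting the best arm when it exceeds the next best by 20%. Then "If the recalculated total sample size is equal or less than 100 then the study will proceed"; otherwise the trial ends. Section 7.d allows stopping if the interim analysis "indicates that the number of subjects required for this trial exceeds #80".

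**The concern.** The regimen taken forward to Phase 3 is the top of four small raw means. At 12 to 25 per arm, unrestricted randomisation can leave the arms with noticeably different mixes of MS and non-MS subjects. If the diagnoses differ in how CSF BDNF changes over three weeks, part of the difference between arms reflects who was allocated rather than how often they cycled.

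The history taken at screening should supply the diagnosis for every subject, so this variation can be removed at little cost. Left in, it either weakens the ranking or inflates the SD that drives the re-estimation. The second matters here because that SD decides whether the trial continues.

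**Working it through.** **Inputs from the documents.** Four arms; 12 per arm at the re-estimation (4 × 12 = 48); 100/4 = 25 per arm at the section 7.c limit; 80/4 = 20 per arm at the section 7.d threshold; 80% correct selection; 20% difference. No SD is given, so neither 48 nor 100 can be derived from a power calculation.

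**Assumptions.** Two classes (MS, other); 25-40% non-MS; equal expected arm sizes; a diagnosis shift in BDNF response of 0, 0.2 or 0.4 of the best mean.

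**1. Case-mix imbalance.** Simulated gap between the highest and lowest of four arms in the non-MS share, without stratification:

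| Per arm | Average gap | Chance of a gap of 25 points or more |
|---|---|---|
| 12 | 25-29 points | 63-72% |
| 25 | 18-20 points | 14-23% |

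Imbalance alone rarely reverses a true 20% difference. For a 25-point gap to cancel it, the diagnosis shift would have to be 0.2/0.25 = 80% of the top mean. The imbalance acts together with ordinary sampling noise.

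**2. Size needed for the selection target.** With one arm ahead of three equal arms, P(correct) = ∫Φ(x + d)³φ(x)dx, where d = δ√n/SD. Setting P = 0.80 gives d = 1.893, so n per arm = (1.893 × SD/0.2)² = 89.6 × SD², with SD as a fraction of the best mean. The largest SD that meets the target is 0.366 at n = 12, 0.472 at n = 20 and 0.528 at n = 25.

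**3. What diagnosis adds to the SD that section 7.c uses.** The pooled within-group variance is the within-diagnosis variance plus p(1 − p) × shift². For p = 0.40 and shift 0.4 the addition is 0.24 × 0.16 = 0.0384.

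- From SD 0.366: √(0.1339 + 0.0384) = 0.415, so n = 89.6 × 0.1723 = 15.4. N is 62 unrounded by arm, or 64 at 16 per arm, against 48.
- From SD 0.528: √(0.2790 + 0.0384) = 0.563, so n = 89.6 × 0.3174 = 28.4. N is 114, or 116 at 29 per arm, against 100.

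The increment is the same in both cases: 4 × 89.6 × 0.0384 ≈ 13.8 subjects. Under this assumption diagnosis alone tips the trial over the 100 limit only when the requirement without it lies between about 86 and 100 (about 66 to 80 under the section 7.d threshold). For a shift of 0.2 the increment is 4 × 89.6 × 0.0096 ≈ 3.4 subjects. For no shift it is zero.

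**4. Probability of correct selection (unadjusted, simulated, 40% non-MS).**

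- Sized on the pooled SD, as section 7.c is written: about 80-81%.
- n held at 12 or 25, or sized on the within-diagnosis SD, with shift 0.4: about 75% or 77%. With shift 0.2 the loss is about 1 point.

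**5. What adjustment buys when n is sized on the pooled SD.** Correct selection rises from 80% to about 81%, 84-85% or 88-89% for diagnosis gaps of 0.5, 1.0 or 1.5 within-diagnosis SDs (MS share 50-70%).

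**The case against.** The strongest objection is that the plan already pays for this noise. The within-group SD in section 7.c contains the variation between diagnoses, so a re-estimate applied as written restores the 80% target. That stands. A reader might infer that correct selection falls from 80% to 75% or 77%. The documents do not support that reading, because it requires a fixed n or an SD taken within diagnosis, and section 7.c prescribes neither.

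The evidence that diagnosis matters is also thin, and this too stands:

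- No BDNF figure by diagnosis is given. A shift of 0.4 is twice the 20% treatment difference.
- The background remark on glial and neuronal sources of BDNF contrasts injured with normal CNS. It does not separate MS from TM or NMO.
- The marked CSF inflammation described for NMO belongs to active relapses, whereas entry requires onset at least three months earlier and medical stability. The quoted difference in recovery is neurological, not a BDNF response.
- Ranking on change removes stable level differences between diagnoses. This helps less at the re-estimation, which section 7.c words in terms of BDNF levels; there such differences would enter the SD.

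Two other strong readings fail. Chance imbalance is not systematic bias. Nor is diagnosis permanently inseparable from dose, since it could be tabulated or adjusted for later from the medical history. Finally, the lack of stratification is inferred from silence, because no randomisation method is described at all.

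**Conclusion.** The point holds as a recommended precision improvement. Diagnosis is absent from the stated randomisation, from the independent variables and from the selection rule. If it influences the change in CSF BDNF, the trial needs more subjects than necessary or may stop when it need not. For a shift of 0.4 of the best mean and 40% non-MS, the cost is about 14 subjects on the formula and up to 16 after rounding to whole arms. A requirement already near the cap would then cross it and end the study. For a shift of 0.2 the cost is 3 to 4 subjects before rounding, and for no shift it is nothing.

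The case mix and the shift are assumptions, and the documents can neither confirm nor exclude them. The case for acting rests on the low cost of the change and on the hard stop in section 7.c, not on a demonstrated difference between diagnoses.

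**What to change.** - Record diagnosis before randomisation, and randomise in small permuted blocks within two strata: MS, and TM/NMO/other.
- In section 7.c, rank the arms on mean change in CSF BDNF adjusted for the stratum. This means specifying a model for the primary outcome, because the plan names analysis of variance only for the other markers.
- Use the residual SD from that same model in the re-estimation, so that removable variation does not count towards the limit.
- Tabulate diagnosis by arm.
- Reconcile the 100-subject limit in section 7.c with the 80-subject threshold in section 7.d, since they set the maximum arm size (25 or 20).

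The cost is two allocation lists, one model term and one degree of freedom, with no extra visits or lumbar punctures. Blocks may be left incomplete in the smaller stratum, so exactly 12 per arm is not guaranteed. If stratified randomisation is not adopted, adjustment alone recovers nearly all of the loss.

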RT300 ergometer (Restorative Therapies, Inc., Baltimore, Maryland) are currently installed at the International Neurorehabilitation Institute (INI) according to INI and Johns Hopkins Hospital safety guidelines. The muscles chosen for stimulation will be the bilateral glutei, quadriceps and hamstrings. The FES stimulation parameters will be set as follows: waveform biphasic, charged balanced; phase duration typically of 250 microseconds; pulse rate 33 to 45 pulses per sec (pps). The stimulus intensity of each channel will be adjusted for individual patients and muscle group so that a tolerable stimulation is provided that will generate a cycling action (0-140 mA). Target cycling speed is 50 RPM. Resistance will be automatically adjusted by the FES bike according to the subject's performance. When fatigue occurs, participants will continue cycling with electrical stimulation and motor support. FES therapy will be administered for one hour per session with a frequency according to the assigned study group (1 to 5 session of FES ergometry per week).

Passive Ergometry

The passive ergometry treatment group will use the same RTI 300 ergometer however during this period of treatment assignment stimulation will not be turned on. Instead, continuous motor support will be activated resulting in passive cycling. Target cycling speed is 50 RPM. Participants assigned to passive ergometry will be required to have one hour of passive therapy 3 times a week for the entire duration of treatment assignment.

Study Assessments

The tests listed below will be performed for all subjects. The data collection schedule in Table 1.

a) Medical History

This is a routine exam. A detailed medical history will be obtained by the study physician including history of present illness, review of systems, current medications, family medical history, social history, and allergies.

b) Physical Exam

This is a routine exam. A study physician will obtain a detailed clinical exam including a standard general medical exam (head, ears-nose-throat, neck, heart, lungs, abdomen, extremities), and neurological exam (cranial nerves, reflexes, American Spinal Injury Association exam).

c) Vital Signs

This is a routine exam. Vital signs will be obtained including blood pressure, heart rate, respiratory rate, temperature, height, and weight.

d) Modified Ashworth Scale (MAS)

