This is a routine exam performed for people with spinal cord injury. Muscle tone will be assessed using the Modified Ashworth Scale (MAS). The MAS is a widely used neurological rating scale, ranging from 0 (normal) to 5 (rigidity). It measures neurological impairment and disability based on the ratings of an observer or neurologist through structured definitions. The MAS will be conducted by the study neurologist at baseline and at the final study visit.

e) Fast Urine Pregnancy Test:

This is a routine exam performed for women of child bearing age who do not take any birth control prophylaxis. Urine samples will be obtained at KKI. The urine (for rapid urine pregnancy testing) will be sent to the Johns Hopkins Medicine (JHM) Pathology lab.

f) Concomitant Medications

This is a routine exam performed for people with spinal cord injury. Concomitant medications will be recorded.

g) FES Trial

This is a routine exam performed for people with spinal cord injury at the ICSCI. Once medically screened to continue participation in the study, subject will undergo a trial use of the FES cycle. This trial of FES will be overseen by a trained physical therapist experienced at setting up the FES cycle. The goal of this will be to ensure that the patient is willing and able to use the cycle.

h) CSF Analyses via Lumbar Puncture

This is a routine procedure with an experimental analysis. Cerebrospinal fluid (CSF) will be collected by one of the study investigators at KKI. Approximately 12-15ml of CSF will be collected during each procedure.

Neural activity triggered by FES may induce an increase in nerve growth factors, or neurotrophins as described in the background section of this document. Such factors, including brain derived neurotrophic

Date: May 10, 2016

Principal Investigator: [name].

Application Number: NA_00041441

factor (BDNF), nerve growth factor (NGF), ciliary neurotrophic factor (CNTF), glial cell line-derived neurotrophic factor (GDNF), neurotrophin-4 (NT4), and neurotrophin-3 (NT3) have been shown to decrease after cessation of neural activity. BDNF has been linked to improved functional outcomes following CNS injury. We therefore chose BDNF as a surrogate marker to determine FES efficacy. In addition to BDNF we will also look at several other neurotrophins and inflammatory markers as noted above.

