Principal Investigator: [name].
Application Number: NA_00041441

Study Assessments:

The following post-consent screening will be performed at the Screening Visit (Week -1):

- a. Medical History (about 30 minutes)
- b. Physical Exam (about 30 minutes)
- c.
- d.
- e. Fast Urine Pregnancy Test (about 15 minutes)
- f.

The subject eligibility criteria will be reviewed after the Screening Visit.

The following assessments will be performed at the FES Trial Visits:

- a. FES trial (about 30 minutes)

The subject eligibility criteria will be reviewed after the FES Trial Visit. Participants who fail the FES trial will be excluded from the study. If the subject is willing and able to proceed with the study the subject will be signed up with "Mood24/7", and scheduled for the Baseline visit.

The following assessments will be performed at the Baseline (Week 0) visit:

- a. Vital Signs (about 5 minutes)
- b. Modified Ashworth Scale (about 15 minutes)
- c. Concomitant Medication (about 10 minutes)
- d. Lumbar Puncture (about 30 minutes)
- e. Blood Draw (about 5 minutes)

The following assessments will be performed at the Final (Week 3) visit:

- a. Physical Exam (about 30 minutes)
- b. Vital Signs (about 5 minutes)
- c. Modified Ashworth Scale (about 15 minutes)
- d. Concomitant Medication (about 10 minutes)
- e. Lumbar Puncture (about 30 minutes)
- f. Blood Draw (about 5 minutes)
- g. Mood assessment review (about 5 minutes)

	Screening	FES Trial	Baseline	Final
	1 ¾ hours	½ hours	1 ¾ hours	1 ¾ hours
Medical History	√			
Physical Exam	√			√
Vital Signs			√	√
Modified Ashworth			√	√
Fast Urine Pregnancy	√			
Concomitant Medications			√	√
FES Trial		√		
Lumbar Puncture			√	√
Blood Draw			√	√
Mood				√

Table 1: Data Collection Schedule

Study Treatment:

The total number of treatment visits depends on the study group:

- Group FES 1: a total of 3 FES ergometry visits scheduled 1 hour, 1 time a week for 3 weeks.
- Group FES 3: a total of 9 FES ergometry visits scheduled 1 hour, 3 times a week for 3 weeks.
- Group FES 5: a total of 15 FES ergometry visits scheduled 1 hour, 5 times a week for 3 weeks.
- Group Passive: a total of 9 passive ergometry visits scheduled 1 hour, 3 times a week for 3 weeks.

Blinding:

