- a) The subject experiences a medical emergency that necessitates discontinuation of therapy
- b) The subject experiences a serious adverse event (WHO Grade IV-V adverse events) that is judged to be likely related to the assigned treatment group or is of severity that warrants discontinuation of assigned treatment.

Date: May 10, 2016
Principal Investigator: [name].
Application Number: NA_00041441

c) For any medical reason at the discretion of the investigator.

Individual participants will be removed from the study if they experience toxicity or complications as described above.

* Subject not compliant:

- Fails to follow directions.
- Are not compliant: participants who miss more than 3 sessions of cycling for the duration of the study.
- Unwilling to perform the second lumbar puncture prior at the end of the study.
- Become pregnant.

8. Risks

a. Medical risks, listing all procedures, their major and minor risks and expected frequency.

The medical risks are defined in the section below. This allows combining the risk and risk management in the same section for each risk.

b. Steps taken to minimize the risks.

All assessments and intervention sessions will be supervised by the Principal Investigator and/or a licensed research Physical Therapist trained in the use of FES.

For all the study procedures, the risks and risk management are defined in the sections below.

Intervention Risks:

FES

The risk associated with FES is pain at the stimulation site. **To minimize the risk**, stimulation will only be done to the participant's tolerance level. There is a minimal risk of skin burn. To further minimize the risk of skin burn, only appropriate size electrodes will be used and they will be replaced as per the manufacturer's recommendations.

The safety of FES for use during pregnancy has not been established. Therefore pregnant women will not be enrolled in the study. **To minimize the risk**, any females who are of child bearing age will be asked to undergo pregnancy testing prior to the start of the study.

Assessment Risks:

Medical History

Aside from the risk associated with disclosing personnel or protected health information outside the research study and possible discomfort with being asked personal questions, there are no known risks associated with this measurement.

Physical Exam

Date: May 10, 2016
Principal Investigator: [name].
Application Number: NA_00041441

There are no known risks associated with this assessment.

Vital Signs

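### The protocol gives two different rules for who has a pregnancy test before FES, and the narrower one leaves out women using birth control

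*Combined protocol and SAP*

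**What the plan says.** Section 4, Study Assessments, item e) describes the fast urine pregnancy test: "This is a routine exam performed for women of child bearing age who do not take any birth control prophylaxis". The sentence introducing that list of assessments says "The tests listed below will be performed for all subjects". The Screening Visit list names the test, "Fast Urine Pregnancy Test (about 15 minutes", without saying who has it. Table 1 marks it at Screening only, again with no qualification.

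Section 8, under the FES intervention risks, gives the reason for testing: "The safety of FES for use during pregnancy has not been established". It continues, "Therefore pregnant women will not be enrolled in the study", and names the mitigation: "any females who are of child bearing age will be asked to undergo pregnancy testing prior to the start of the study".

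Pregnancy is an exclusion criterion in section 5. It is also a ground for removing a participant, both in section 4 and in section 7 d.

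**The concern.** The two rules cover different groups. Section 8 includes every female of child-bearing age. Section 4 e) includes only those not using birth control. Section 4 is where staff look to see what to do, and item e) is the only text there that says which women are tested. Someone following it could reasonably skip a contraception user.

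What is at stake is participant safety. The protocol treats pregnancy as a reason not to give FES and offers the test as its safeguard. The exclusion and removal rules can act only on a pregnancy that someone has recognised. For an untested woman, recognition before the first stimulation would depend on the history and physical examination at screening, and an examination is no substitute for a test. The protocol does not define what counts as birth control, and section 5 sets no contraception requirement that might justify an exemption.

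**Working it through.** There is no planned figure to reproduce. The check is a comparison of every place that deals with pregnancy testing, followed by a count of scheduled exposure.

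**Step 1. Who is tested, by location**

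| Place | Group tested | Contraception exemption |
|---|---|---|
| Section 4, lead-in to the assessments | All subjects (cannot be literal, since men are eligible) | None |
| Section 4 e) | Women of child-bearing age not using birth control | Yes |
| Section 4, Screening Visit list | Not stated | None |
| Table 1 | Not stated | None |
| Section 8, FES risks | Any female of child-bearing age | None |
| Section 8, Pregnancy testing | Not stated (deals with disclosure of a positive result) | None |

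**Step 2. Apply both rules to one woman.** Take a woman of child-bearing age who uses contraception. Under section 4 e) she is not tested. Under section 8 she is asked to test. No other text decides between the two, and none offers an alternative check for her.

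**Step 3. Would a later test catch it?** Table 1 has four assessment visits (Screening, FES Trial, Baseline, Final). The test is marked at one of them, Screening. A woman missed there has no further scheduled test.

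**Step 4. Scheduled FES time for a woman missed at screening.** The trial visit is listed as "FES trial (about 30 minutes", and every participant has it whatever her later arm. Treatment sessions last 1 hour; the highest dose is "a total of 15 FES ergometry visits scheduled 1 hour, 5 times a week for 3 weeks". Scheduled hours = 0.5 + (number of FES sessions × 1):

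- Passive: 0.5 + 0 = 0.5 h
- FES1: 0.5 + 3 = 3.5 h
- FES3: 0.5 + 9 = 9.5 h
- FES5: 0.5 + 15 = 15.5 h

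The 0.5 h is the length of the trial assessment, which includes setting up the cycle, so time under stimulation at that visit may be shorter. These are scheduled times. They do not measure risk or the number of women affected.

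**The case against.** The best defence is that item e) was never meant as a restriction. Entries in that list open with a label saying whether the procedure is routine care. The Modified Ashworth, concomitant medication and FES Trial entries call themselves routine for people with spinal cord injury, although the trial enrols people with inflammatory myelopathy. Read that way, item e) says in whom the test is usually done, and section 8 says who is tested in this study. The lead-in, the visit list and Table 1 carry no exemption, so staff working from the schedule would probably test everyone eligible. Contraception users would also be expected to have a lower chance of pregnancy, and the exclusion covers them regardless.

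This reading is plausible, but it does not settle the matter. If item e) only describes usual practice, section 4 never says which women are tested. The contraception clause also has no counterpart in the other entries and reads naturally as a limit. The points about size stand: the group is restricted, the probability is unknown, and eligibility is reviewed after both the Screening and FES Trial visits. It is also fair to say that the exposure hours show what a missed woman would be scheduled to receive, not how likely a miss is. The single scheduled test makes a miss at screening matter more, but repeat testing is a separate question that is not raised here.

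**Conclusion.** The inconsistency is real, and the conclusion is firm on the wording: two current sections define the tested group differently and nothing reconciles them. Whether any woman would actually go untested depends on which section staff follow, so the claim is only that contraception users may be missed. The effect is confined to women of child-bearing age using birth control. The documents give neither their number nor their chance of an unrecognised pregnancy, so no expected count can be calculated. A missed woman would be scheduled for between 0.5 h and 15.5 h of FES depending on arm, with the trial visit counted in full. The CSF BDNF comparison, the selection rule and the sample size re-estimation are not affected. The point should be corrected because the protocol's own stated safeguard may not reach everyone it was written for.

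**What to change.** In section 4 e), delete the closing clause that limits the test to women not taking birth control, and state that all women of child-bearing age are tested at screening, before the FES Trial visit, regardless of contraception. Add a footnote to the pregnancy-test row of Table 1 naming that group, and use the same definition in section 8. This adopts the standard that section 8 already sets.

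The cost is one deleted clause, one footnote and matching wording in section 8, plus a few more urine tests of about 15 minutes each at a visit that already includes the test.
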